	Product: Teleflex Arrow Vascular Positioning System G4
	Development Phase: Post Market
Title: Vascular Positioning System G4 Algorithm ECG Data Collection for Model Training Study, A Single Center Prospective Clinical Study	
Investigators: [name] [name], RN Duke University Hospital	Sponsor Management: Teleflex Incorporated Study Management: [name] PhD, Clinical Trial Manager Study Monitor: [name], Clinical Research Associate
Study Design: Prospective Clinical Study	
Objective: The objective of this study is to collect and analyze intravascular and extravascular echocardiogram (ECG) data from subjects receiving peripherally inserted central catheters (PICC) while using the Vascular Positioning System G4 and a 12 lead ECG machine. The data obtained will be used to evaluate the correlation between intra- and extravascular ECG data and determine usability in updating the G4 algorithm.	
Primary endpoint: The primary endpoint is synchronized digital data collected from the G4 and ECG machines during the PICC insertion procedure, including a photographic image documenting ECG lead placement, and a chest x-ray (post procedure).	
Number of Subjects:30	Number of Study Centers: 1
Duration of Evaluation: Time required for PICC insertion	Estimated Duration of Study: 4 months

Contents

1. Introduction	5
2. Objective of Study and Study Design	6
3. Selection of Subjects.....	6
4. Study Procedures.....	7
5. Assessment of Safety	11
6. Potential Risks and Benefits.....	13
7. Statistical Consideration	14
8. Quality Control and Quality Assurance	14
9. Study Monitoring	15
10. Institutional Review Board Review.....	15
11. Data Handling and Recording.....	16
12. Confidentiality	17
13. Publication Policy.....	17
References	18

1. Introduction

1.1. Background

A peripherally inserted central catheter (PICC) is an intravenous device that can be successfully utilized for medium- and long-course intravenous therapy in hospitalized and discharged patients.ⁱ Correct positioning of a PICC is essential to avoiding complications.ⁱⁱ The Arrow Vascular Positioning System G4 (here forth referred to as G4) (Teleflex, Morrisville, NC, USA) is designed for PICC navigation and tip confirmation. Using a combination of intravascular Doppler ultrasound, intravascular electrocardiogram (ECG) and advanced algorithmic logic, the system measures multiple physiological parameters and provides real-time navigation as the PICC advances through the patient's vasculature.ⁱⁱⁱ

Like all medical devices, the AI ECG (algorithms) must be carefully vetted and validated in real-world clinical environments.^{iv} Machine learning creates algorithms by building a model from a set of data points, then verifying its accuracy. Increasing data points allows the device to learn various circumstances and thus the ability to compare and respond appropriately.

This study seeks to collect and analyze synchronized digital data collected from the G4 and ECG machines during the PICC insertion procedure. De-identified G4 and ECG data will be submitted to the sponsor. Photographic data confirming ECG lead placement and radiographic imaging (chest x-ray) showing PICC placement will also be de-identified and submitted to the sponsor. Both the G4 and the ECG machine used for data collection in this study are FDA cleared.

1.2. Study Rationale

The purpose of this study is to collect and analyze synchronized intra- and extravascular ECG data from subjects requiring PICC insertion using the G4 system and an external 12-lead ECG machine. This study will serve to determine the feasibility of using the comparison data collected to evaluate the correlation between intra- and extravascular ECG data, and to determine usability of the data in refining the next generation G4 system algorithm.

1.3. Hypothesis

Data collected simultaneously from the G4 system and a 12-lead ECG machine during PICC insertion in adult subjects will be useful in evaluating the correlation between intra- and extravascular ECG recordings and refining the next generation G4 algorithm model.

1.4. Description of Device

The Arrow G4 system is an FDA cleared device (K123813) indicated for use as an alternative method to fluoroscopy or chest x-ray for central venous catheter tip placement confirmation in adult patients. The system consists of a base unit powered by a proprietary algorithm, a touch screen interface with remote control, a Doppler enabled ultrasonic stylet,

and a power supply; that are used together during PICC insertion to guide the inserter through the anatomy of the vasculature to the proper catheter tip location in the lower 1/3 of the superior vena cava – cavo-atrial junction.

An FDA cleared 12-lead ECG machine capable of collecting ECG data digitally with a sample resolution between 12-16 bit at a sample rate of 300 - 1000 Hz will be utilized for this study.

Photo documentation will be captured using a digital camera.

Radiographic image (lateral chest x-ray) will be captured using Duke Radiology services to document PICC tip placement.

2. Objective of Study and Study Design

2.1. Primary Objective

The objective of this study is to collect and analyze synchronized intra- and extravascular ECG data from subjects receiving PICC insertion while using the G4 and a 12-lead ECG machine. The data will be analyzed to evaluate the correlation between intra- and extravascular ECG data.

Primary Endpoint

The primary endpoint is the successful collection of the following data: synchronized digital data collected from the G4 and ECG machines during the PICC insertion procedure, photographic images documenting ECG lead placement, and a chest x-ray of the inserted PICC (post procedure). A copy of the data will be submitted to the sponsor.

2.2. Study Design

This is a single center prospective clinical feasibility study. All enrolled subjects will receive a 12-lead ECG during PICC insertion, a chest x-ray post insertion, and a photographic documentation of ECG lead placement.

2.3. Duration of Subject Study Participation

Each subject's participation will start at the time of signing the informed consent and terminate upon completion of the x-ray.

3. Selection of Subjects

3.1. Participant Population

Adult male patients scheduled to receive a PICC insertion using the G4 tip navigation system may be considered for participation in the study.

As this is a feasibility study, male and female patients will be recruited for participation in this study. As a means to limit female exposures to photographs, Images will only be captured for male subjects

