3.3. Inclusion Criteria

Subjects must meet the following criteria to be selected for participation in the study:

- 22 years of age or older
- Scheduled for PICC insertion using the G4 system
- Willing to allow thoracic photos to be obtained after ECG lead placement

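### Section 3.1 admits only men in one sentence and both sexes in the next, and under either reading the photograph rule leaves no woman evaluable

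*Combined protocol and SAP*

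**What the plan says.** Section 3.1 makes two statements about who may enter. The first is "Adult male patients scheduled to receive a PICC insertion using the G4 tip navigation system may be considered for participation in the study". The second paragraph says: "As this is a feasibility study, male and female patients will be recruited for participation in this study". The same paragraph then restricts photography: "Images will only be captured for male subjects".

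Elsewhere the population is not limited by sex. The hypothesis in 1.3 concerns "Data collected simultaneously from the G4 system and a 12-lead ECG machine during PICC insertion in adult subjects", and 1.4 gives the device's indication as "central venous catheter tip placement confirmation in adult patients". The inclusion list in 3.3 sets an age limit, "22 years of age or older", and neither 3.3 nor 3.4 names sex. Section 4.4.4 collects gender, and 4.3 and 4.3.1 reserve photographs for some consenting men.

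Three rules decide who counts. Section 3.2 enrols up to 30 to obtain 20 evaluable subjects, and its definition of evaluable includes a captured photograph of lead placement. Section 3.3 requires every subject to be "Willing to allow thoracic photos to be obtained after ECG lead placement". Section 7.2.2 excludes non-evaluable subjects from the feasibility analysis.

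**The concern.** The two statements in 3.1 cannot both define the candidate population. A site that acts on the first recruits no women, although the hypothesis and the device's indication cover adults generally. A site that acts on the second recruits women whom the first does not admit, and 9.2 treats any noncompliance with the protocol as a deviation.

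The photograph rule adds to the problem. Even if the conflict is settled in favour of both sexes, the evaluable definition asks for something that 3.1 says will not be obtained from a woman. Women would be consented and would undergo the 12-lead recording and the chest x-ray, and would then be left out of the feasibility analysis. At stake are the scope of the conclusion, the use made of women's participation, and whether 20 evaluable subjects can be reached within 30 enrolments.

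**Working it through.** The plan gives no figure on this point to reproduce. Section 7.1 says the sample size is not statistically justified, and no sex split is stated.

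**Step 1: the two readings side by side**

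| | First sentence of 3.1 | Second paragraph of 3.1 |
|---|---|---|
| Women enrolled | 0 of up to 30 | allowed |
| Women photographed (3.1, 4.3) | 0 | 0 |
| Women evaluable (3.2) | 0 of 20 | 0 of 20 |
| Women in the feasibility analysis (7.2.2) | 0 | 0 |
| Women in the safety population (7.2.1) | 0 | those in whom data collection was started |

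The readings differ in enrolment and in the safety population. They do not differ in the feasibility set.

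**Step 2: reaching 20 evaluable subjects when women are enrolled**

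Inputs: cap n = 30 and target 20 (3.2); female share f among those enrolled (assumed). The favourable case is taken, in which every enrolled man is evaluable. The number of evaluable subjects is then the number of men, X ~ Binomial(30, 1 − f), and the quantity needed is P(X ≥ 20).

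| f (assumed) | Expected men, 30(1 − f) | P(X ≥ 20) |
|---|---|---|
| 0 | 30 | 1 |
| 0.20 | 24 | 0.97 |
| 0.30 | 21 | 0.73 |
| 1/3 | 20 | 0.58 |
| 0.40 | 18 | 0.29 |
| 0.50 | 15 | 0.05 |

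These chances are upper limits for each f. Any man with an incomplete recording or no x-ray lowers them, and so does the wording in 4.3 that only some consenting men are photographed. Even with no women enrolled, 20/30, or two thirds, of the men would have to be photographed.

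**Step 3: replacement**

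Section 3.2 says non-evaluable subjects are replaced. If replacement stays within the cap of 30, the table applies. If it may go beyond the cap, the average enrolment needed for 20 evaluable men is 20/(1 − f): 20/0.6 = 33.3 at f = 0.40 and 20/0.5 = 40 at f = 0.50. Both exceed 30.

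**The case against.** The strongest reply is that the first sentence is a stray word that would not mislead anyone. Section 4.1 has staff approach patients who meet the eligibility criteria, and 4.2 ties enrolment to those criteria, which do not mention sex. The first sentence is permissive and the second paragraph directive. There is one centre, so sites cannot diverge. A woman who meets 3.3 and 3.4 has been included properly, so the deviation risk is slight. This is also a feasibility collection: the hypothesis is only that the data will be useful, and no error rate or power is affected.

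Most of that stands. The male-only wording is the outlier, the site may well recruit women anyway, and the deviation risk is small. But no section withdraws the sentence, and the reply does not touch the photograph rule. That rule applies most directly when the site does what the rest of the protocol implies.

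A reader might infer that following the second paragraph, or deleting the one word, would bring women into the 20 evaluable subjects in proportion to their share of PICC candidates. The documents do not support that. Sections 3.1, 3.2 and 7.2.2 together put the number of evaluable women at zero whatever the enrolled share. Deleting the word alone would confirm the enrolment of women who cannot count and could use up the 30 places.

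**Conclusion.** Section 3.1 contradicts itself on who may be enrolled, and the text needs amending. As written, the feasibility set contains no women under either reading, so its conclusion would rest on men while the hypothesis and indication refer to adults. If both sexes are enrolled, the target of 20 within 30 is also at risk: the chance is about 0.73 at 30% women, 0.29 at 40% and 0.05 at 50%. Those figures assume the stated female shares, independent enrolment, full evaluability of men and a binding cap of 30. At 20% women the chance is 0.97, so the risk depends on a sex mix that the documents do not give.

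A reader might also infer that the study's data as a whole are invalid for adults. That goes too far. The study makes no inferential claim, and women's recordings, if collected, could still be examined outside the evaluable set. The effect is on the scope of the feasibility conclusion and on reaching the target, not on an estimate or an error rate.

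**What to change.** Make these changes in one amendment, because the first alone would not help:

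1. Delete *male* from the first sentence of 3.1.
2. In 3.2, accept the primary and secondary lead-placement attestation, which 4.3.1 already requires for each subject, as sufficient documentation where no photograph is taken.
3. Align the other photograph wording: 2.2, which promises a photograph for all enrolled subjects; the willingness criterion in 3.3 and its counterpart in 3.4; and the primary endpoint in 2.1 and the synopsis, which also lists photographs.

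Any subject with complete G4 and ECG recordings and the x-ray is then evaluable regardless of sex, and the female share no longer affects whether 20 is reached. No subjects or procedures are added. The cost is the amendment and its IRB review, plus one small loss: in unphotographed subjects lead placement is documented by attestation only, so the report should give the number documented each way.

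If the sponsor does intend men only, 3.3 should say so, the second paragraph of 3.1 should be removed, and the feasibility conclusion should be limited to men.

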3.2. Sample Size

A sample size of up to 30 adult subjects will be enrolled to obtain 20 evaluable subjects. Including a maximum of 10 subjects in whom the G4 system was used for tip navigation but the blue bull's eye was not achieved and 10 subjects where the blue bull's eye served as confirmation for tip placement. An adult subject per The Federal Food, Drug, and Cosmetic Act (FD&C Act) is persons 22 years of age and older at the time of treatment.^{vi} To be considered an evaluable subject, data must be collected for the duration of the PICC insertion procedure on both the G4 and the ECG machines, the post-insertion chest x-ray completed, and photographic documentation of the ECG lead placement captured. Non-evaluable subjects will be replaced to meet the target sample size.

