4.4. PICC Insertion, ECG, Chest X-ray, and Data Collection

The ECG recording and chest x-ray will be performed as described in the sections below. The ECG machine should start recording data prior to the first skin puncture and continue recording through catheter tip placement.

The study staff will defer to the institution's policy for confirming proper tip placement.

After successful PICC tip placement , ECG data collection can be terminated. Up to a maximum of 10 subjects in whom the blue bull's eye was not achieved during PICC navigation will be included as evaluable subjects. Beyond, these 10 subjects, **if the blue bull's eye is not achieved the subject's participation in the study will be terminated and no additional study procedures will be performed.** If an ECG lead should fall off during the data collection period, the lead can be replaced, as long as, the G4 system is not displaying the orange caution indicator on the screen. If the caution indicator is displayed refrain from replacing the lead. If the ECG stops recording during the data collection period, it will not be resumed.

Data Collection Procedures

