5.2.5. SAE Reporting

Serious adverse events must be reported to the sponsor immediately, within 24 hours of knowledge of the event, if it occurs or comes to the attention of the investigator any time a subject is on study or reported to the investigator subsequent to the subject's participation. SAEs may be reported by emailing the SAE documents to:

Teleflex Incorporated
Global Clinical Operations
Email: [contact]

An SAE report form and relevant documentation (if any) should be submitted electronically to Teleflex and to the IRB, in accordance with IRB reporting requirements. The initial report should include at minimum the following information:

- Subject ID number, sex, age
- Study device/procedure suspected relationship to the SAE

- SAE term and date of event

Follow-up information including causality, severity, outcome, action taken, and concomitant medications should be communicated to the sponsor as soon as possible.

6. Potential Risks and Benefits

For the purpose of this study, subjects will have continuous 12-lead ECG tracings performed during PICC insertion and one chest x-ray of the inserted catheter at the end of the procedure. The chest x-ray and 12-lead ECG are not part of the routine PICC insertion procedures. These risks are outlined further but are considered to be minimal risk procedures. There is no perceived clinical benefit to subjects from participation in this study.

There are standard risks of participating in a research study, for example given the potential of accidental disclosure of subject's confidential information. Every effort will be made to ensure that subject personal information remains confidential at all times, including application of Subject ID and redacting personally identifying information before submitting to the Sponsor.

Since subjects participating in the study will be receiving PICC insertion per standard of care, and the G4 is within the standard procedures for use during PICC device placement at this institution, these are not considered study procedures. Consent for PICC placement will be obtained as part of the standard of care and will not be associated with this study.

The internal G4 device records ECG data during the central catheter line insertion that is used to detect correct placement. This ECG recording will be de-identified of the subject PHI and replaced with subject number prior to being sent to Teleflex.

Risks associated with 12-lead ECG:

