7.2.2. Feasibility Analysis Population

Non-evaluable subjects will be excluded from the feasibility analysis population. See Section 3.2 - Sample Size for definition of evaluable subject.

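### Does the unlabelled 10 for bull's-eye subjects in Section 3.2 leave open when enrolment stops?

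*Combined protocol and SAP*

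**What the plan says.** Section 3.2 sets the overall numbers: "A sample size of up to 30 adult subjects will be enrolled to obtain 20 evaluable subjects". It then describes the make-up of the 20. The first group, limited to a maximum of 10, had G4 navigation without reaching the bull's eye. The second is 10 subjects in whom it confirmed the tip position; the two are joined in the words "blue bull's eye was not achieved and 10 subjects where the blue bull's eye served as confirmation for tip placement". The same section defines an evaluable subject by complete G4 and ECG recordings, the chest x-ray and the lead photographs. Bull's-eye status is not part of that definition. Non-evaluable subjects are to be replaced until the target is met.

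Section 4.4 gives the operational rule: "Up to a maximum of 10 subjects in whom the blue bull's eye was not achieved during PICC navigation will be included as evaluable subjects". After those 10, a subject who does not reach the bull's eye leaves the study with no further study procedures. There is no matching rule for subjects who do reach it.

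Section 7.1 repeats the figure of 20 evaluable without a split and says that the sample size has no statistical justification. Section 7.2.2 states: "Non-evaluable subjects will be excluded from the feasibility analysis population". For the definition it points back to Section 3.2.

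**The concern.** The two tens add up to exactly 20, so a reader could take Section 3.2 as a fixed 10/10 split. Section 4.4, which limits one group only, reads instead as any mix of 20 with no more than 10 lacking the bull's eye.

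The two readings would have staff act differently. Suppose 18 subjects with the bull's eye and 2 without have been enrolled, all evaluable. Under Section 4.4 the study is complete. Under a fixed split only 10 + 2 = 12 places are filled, and 8 more subjects without the bull's eye must come from the 10 enrolments left.

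Any extra enrolment exposes people to research procedures. Section 2.2 says "All enrolled subjects will receive a 12-lead ECG during PICC insertion, a chest x-ray post insertion". Section 6 adds that "The chest x-ray and 12-lead ECG are not part of the routine PICC insertion procedures" and that "There is no perceived clinical benefit to subjects from participation in this study". The status of an eleventh bull's-eye subject in the feasibility population might also seem open.

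**Working it through.** **The plan's own figure.** 10 + 10 = 20, so the total reproduces. The ceiling allows 1 − 20/30 = one third of enrolled subjects to be non-evaluable.

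**The passages side by side.**

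1. The no-bull's-eye number is a maximum in both 3.2 and 4.4. A maximum may be under-filled; a design that needs exactly 10 contradicts the word in both places.
2. The target in 3.2 and 7.1 is 20 evaluable. Replacement in 3.2 applies to non-evaluable subjects only. Nothing provides for enrolling beyond 20 evaluable to fill one group.
3. With a total of 20 and at most 10 without the bull's eye, the number with it must lie between 20 − 10 = 10 and 20 − 0 = 20. The second 10 is thus the floor that the other two numbers already imply.
4. Evaluability in 3.2 ignores bull's-eye status, and 7.2.2 excludes only the non-evaluable. An eleventh complete bull's-eye subject is therefore in the feasibility population.

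**What the reading would be worth.** Let f be the chance of not reaching the bull's eye and e the chance of being otherwise evaluable. Neither is in the documents, so both are assumed. Let B and X be the running counts of evaluable subjects with and without the bull's eye. Enrolment is followed one subject at a time, exactly, up to 30.

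- Section 4.4 reading: stop when B + min(X, 10) = 20.
- Fixed reading: stop when B ≥ 10 and X ≥ 10.

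Mean number enrolled, fixed reading against Section 4.4 reading:

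| f | e = 1 | difference | e = 0.67 | difference |
|---|---|---|---|---|
| 10% | 30.0 vs 20.0 | 10.0 | 30.0 vs 28.4 | 1.6 |
| 20% | 29.8 vs 20.0 | 9.8 | 30.0 vs 28.4 | 1.6 |
| 30% | 28.2 vs 20.0 | 8.2 | 29.9 vs 28.4 | 1.5 |
| 40% | 25.0 vs 20.4 | 4.7 | 29.6 vs 28.6 | 1.1 |

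Differences are taken before rounding. At f = 50% and e = 1 the means are 23.4 and 21.7, a difference of 1.7. At e = 0.8 and f = 20% they are 30.0 and 25.0, a difference of 5.0.

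The chance of completing within 30 enrolled also differs. With e = 1 the fixed reading completes only if 10 ≤ X ≤ 20 among 30 subjects, with X binomial(30, f). That gives 0.0005, 0.06, 0.41 and 0.82 at f = 10%, 20%, 30% and 40%. The Section 4.4 reading needs only X ≤ 20 and gives at least 0.999 throughout. At e = 0.67 and f = 20% the chances are 0.004 and 0.60.

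**A third reading** is 10 fixed with the bull's eye and up to 10 without, stopping at the tenth bull's-eye subject. At f = 20% and e = 1 this stops after 12.5 enrolled on average. It can leave fewer than 20 evaluable, which conflicts with the target in 3.2 and 7.1.

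**The case for a change.** The strongest case for a change is that no sentence says what the second 10 is, that 10 + 10 = 20 invites a quota, and that a clarifying line costs almost nothing. If the bull's eye is usually reached and nearly everyone is evaluable, a site working to a quota would enrol close to 30 rather than 20. It would give up to about 10 more people a non-routine x-ray, and would still probably miss 10/10.

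The missing label is real, and so is the gap in the chance of completion. The rest is weaker. The quota has to be read into the text against the word for a maximum in two sections, and no enrolment or replacement rule supports it. The figure of 10 extra subjects needs an evaluable share near 100%, whereas the plan allows for a one-third loss. Section 6 describes the added procedures as minimal risk.

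The photograph condition does not strengthen the case. Section 3.1 says "Images will only be captured for male subjects", while 3.2 makes photographs part of evaluability. If only 60% of subjects were photographed, the Section 4.4 reading itself would reach 20 with probability 0.29 at f = 20%. That follows from the photograph rule and is a separate matter.

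**Conclusion.** The wording in Section 3.2 is loose, but the plan can be followed as it stands. Sections 3.2, 4.4 and 7.1 together give one workable rule: stop at 20 evaluable, of whom at most 10 lack the bull's eye, or at 30 enrolled. This is a detail that the study team can fill sensibly from the text, and the feasibility population in 7.2.2 is not affected.

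If a site did adopt a fixed split, the mean excess would be about 5 to 10 subjects with full evaluability and failure rates of 10% to 40%. It would be about 1.1 to 1.6 with an evaluable share of 0.67, and 1.7 at a 50% failure rate with full evaluability. All of these rest on rates that the documents do not give, and none takes enrolment past 30. Because Section 7.1 claims no statistical basis for the sample size, no inference is put at risk.

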4.3. ECG Lead Placement Image Capture

ECG lead will be placed according to the standardized ECG lead placement chart below. A second study team member will confirm and attest to the proper placement of the ecg lead in accordance with the ECG lead placement chart below. For some male subjects who consent, the placement of thoracic ECG leads will be documented by three photographs: one photo capturing the chest perpendicular to the xiphoid process, and one left and right oblique photograph. A ruler should be placed in the photograph, not obscuring any ECG leads, as a scale reference. Images captured will exclude portions of the body above the shoulders.

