4.3.1. ECG Lead Placement and Procedure

The subject identification number will be entered into the ECG machine to ensure the correct subject data can be identified. (See below for ECG lead placement.)

ECG 12 lead placement:

Standardized placement of ECG leads is important. ECG lead placement must be consistent between subjects and performed according to the directions provided in this section below. Primary and secondary ecg lead placement attestation will be used to document the lead placement for each subject, to confirm the accuracy of the lead placement with the requirements of the protocol. Some consenting male subjects will undergo photographic documentation of ECG leads.

ECG Lead	Anatomical Placement
Lead 1	Fourth intercostal space on the right sternum
Lead 2	Fourth intercostal space on the left sternum
Lead 3	Midway between placement of Lead 2 and Lead 4 fifth intercostal space at the midclavicular line
Lead 4	Fifth intercostal space at the left and mid clavicular line
Lead 5	Anterior axillary line on the same horizontal level as Lead 4
Lead 6	Mid axillary line on the same horizontal level as Lead 4 and Lead 5
Right Arms (RA)	Anywhere between the right shoulder and right elbow
Right Leg (RL)	Anywhere between the right torso and the right ankle
Left Arm (LA)	Anywhere between the left shoulder and the left elbow
Left Leg (LL)	Anywhere between the left torso and the left ankle

Note: There will be three "duplicate" electrodes (RA / LA and RL) between the two systems (G4 and 12-lead ECG). Duplicate electrodes should be placed as close together as possible without interfering with the other electrode.

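### Evaluability requires a lead-placement photograph that the protocol takes only from some men, so no woman and no unphotographed man can enter the feasibility analysis

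*Combined protocol and SAP*

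**What the plan says.** Section 3.2 plans up to 30 enrolled subjects to obtain 20 evaluable ones. Its conditions for being evaluable are joined by *and*: G4 and ECG data for the whole insertion, plus "the post-insertion chest x-ray completed, and photographic documentation of the ECG lead placement captured". There is no exception by sex. The same section adds: "Non-evaluable subjects will be replaced to meet the target sample size". Section 7.2.2 takes its definition from 3.2: "Non-evaluable subjects will be excluded from the feasibility analysis population".

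The rules on who is photographed differ from one section to another:

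- Section 3.1 opens with "Adult male patients scheduled to receive a PICC insertion using the G4 tip navigation system", then says that "male and female patients will be recruited for participation in this study", and then that "Images will only be captured for male subjects".
- Section 4.3 is narrower still: "For some male subjects who consent, the placement of thoracic ECG leads will be documented by three photographs". Section 4.3.1 repeats the restriction to some consenting men.
- The synopsis and Section 2.1 make the photograph part of the primary endpoint. Section 2.2 says every enrolled subject has one, and Section 6 describes it as something that will be done.
- Sections 3.3 and 3.4 require every subject, women included, to be willing to have thoracic photographs.

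One form of lead-placement documentation does cover everybody. Section 4.3.1 states: "Primary and secondary ecg lead placement attestation will be used to document the lead placement for each subject". That attestation appears in neither the evaluable definition nor the primary endpoint.

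**The concern.** The definition of the analysis set depends on an item that the procedures withhold from a whole group of recruited subjects. A woman can meet every eligibility criterion, have complete G4 and 12-lead recordings, have the x-ray and have her lead placement attested by two people, yet still be non-evaluable. The same holds for any man who is not photographed.

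Three things are at stake:

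- **Who is analysed.** Both sexes are recruited, but the feasibility analysis, which is the purpose of the study, would contain only men. Read literally, no woman can meet the primary endpoint in Section 2.1 either.
- **Needless procedures.** Section 6 says the 12-lead ECG and the x-ray are not routine for PICC insertion and that subjects gain no perceived clinical benefit. Each exclusion for want of a photograph leads to a replacement who has both.
- **An undeclared choice.** The sections cannot all be followed, so staff and analysts would have to pick a rule themselves, possibly after seeing the data.

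Power is not affected, because Section 7.1 does not claim a statistical basis for the sample size.

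**Working it through.** **1. Who can be evaluable.** Apply the definition in 3.2 to the photograph rules in 3.1, 4.3 and 4.3.1.

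| Subject with complete ECG, G4 and x-ray | Photograph taken? | Evaluable (3.2) | In feasibility set (7.2.2) |
|---|---|---|---|
| Man, photographed | yes | yes | yes |
| Man, not photographed | no | no | no |
| Woman | no (3.1) | no | no |

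Evaluable women: 0. This needs no assumption.

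**2. The plan's own figures.** There is no power calculation to reproduce. The stated yield is 20 of up to 30, so 20/30 = 66.7% of enrolled subjects must be evaluable. The room for losses of every kind is 30 − 20 = 10. An 11th non-evaluable subject leaves at most 30 − 11 = 19.

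**3. Chance of reaching 20 within 30.** Let r be the share of enrolled subjects who are photographed men: r = (1 − share of women) × (share of men photographed). The protocol gives neither factor, so r is assumed. Assume also no other data loss and independent enrolment. Then the number evaluable, X, is binomial and

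P(X ≥ 20) = Σ from k = 20 to 30 of C(30, k) r^k (1 − r)^(30 − k).

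| r | Expected evaluable, 30r | P(X ≥ 20) |
|---|---|---|
| 0.40 | 12 | 0.003 |
| 0.50 | 15 | 0.049 |
| 0.60 | 18 | 0.29 |
| 0.70 | 21 | 0.73 |
| 0.80 | 24 | 0.97 |

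The probability reaches 0.80 at r of about 0.72. Two examples of how r arises:

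- Half women and every man photographed: r = 0.50 × 1 = 0.50.
- One quarter women and three quarters of men photographed: r = 0.75 × 0.75 = 0.5625, which gives 16.9 expected evaluable and P = 0.17.

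**4. If replacement may go past 30.** Section 3.2 does not say whether it may. Enrolment until the 20th evaluable subject is then negative binomial, with mean 20/r and mean non-evaluable count 20/r − 20.

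| r | Expected enrolment | Of whom non-evaluable | 90th percentile of enrolment |
|---|---|---|---|
| 0.50 | 40 | 20 | 48 |
| 0.60 | 33.3 | 13.3 | 40 |
| 0.70 | 28.6 | 8.6 | 33 |
| 0.80 | 25 | 5 | 28 |

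**5. What is left out.** The limit in 3.2 and 4.4 on subjects without the blue bull's eye, and any ECG, G4 or x-ray failure, could only lower the probabilities in step 3.

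**The case against.** The best defence is that several sections treat the photograph as universal. Section 2.2 says all enrolled subjects have one, and 3.3 and 3.4 admit only people willing to be photographed. On that reading, the phrase in 4.3 about consenting men could cover nearly every enrolled man, so unphotographed men may be few or absent. This has force as to how many such men there would be. It does not help women, because 3.1 expressly limits images to men, and nothing in 3.2 exempts them. Section 4.4 calls up to 10 subjects without the blue bull's eye evaluable, but that concerns the bull's eye and does not waive the photograph.

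A second objection is that r has no source in the protocol and that one site screening in sequence can steer its mix. If the site enrolled only men and photographed all of them, the shortfall would vanish. That is right, and the probabilities are illustrations, not forecasts. But that route abandons the stated recruitment of women.

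Third, the study is descriptive, excluded subjects' data still go to the sponsor (4.4.2), and they count for safety (7.2.1). This limits the harm to the feasibility set, the endpoint and the extra x-rays. It does not make the definition workable.

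Finally, the attestation may have been meant to take the photograph's place. No section says so. If it was, the definition should be changed to match.

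**Conclusion.** The concern holds and should be fixed before the definition is applied. Two results rest on the text alone: no woman can be evaluable, and, if 30 is a ceiling, no more than 10 enrolled subjects can be non-evaluable for any reason. The target therefore needs at least 20 photographed men among 30, which the protocol neither plans nor ensures. The probabilities, from 0.003 at r = 0.40 to 0.97 at r = 0.80, depend on an assumed r, independent enrolment and no other losses. They show how sensitive the target is to the photograph rule. The conclusion about unphotographed men is conditional: any such man is excluded, but their number is unknown.

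**What to change.** In Section 3.2, replace the photograph condition with completion of the primary and secondary lead-placement attestation, and make the photograph a supplementary item for consenting men. Then bring into line the synopsis endpoint, Sections 1.1, 1.4, 2.1 and 2.2, the first sentence of 3.1, the photograph criteria in 3.3 and 3.4, and the photograph risk text in Section 6.

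The photograph is part of the primary endpoint, so the sponsor may judge images essential. In that case it should keep the condition, restate the population as those who will actually be photographed, and rework the 20-of-30 yield to match. Under either option, state whether replacement may take enrolment past 30.

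The cost is a protocol amendment touching the primary endpoint, eligibility and the evaluable definition, with IRB approval before implementation (Section 10.3). The attestation route adds no procedure and leaves all 10 spare places for ECG, G4 or x-ray failures. Its drawback is that lead position in unphotographed subjects rests on the attestation and the lead locations recorded under 4.4.2 and 4.4.4, without the three-view image with a ruler for scale.
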